Project title: Glucose Control in Type 2 Diabetes in Pregnancy**Principal investigator:**

[name]
 [name]
 E-mail: [contact]

Co-Investigators: [name], MA; [name]

Institution: Department of Obstetrics and Gynecology, Eastern Virginia Medical School, Norfolk, Virginia

1. Background:

Pregestational diabetes mellitus affects 1-2% of all pregnancies in the United States each year, and the incidence continues to increase at an accelerated rate. From 2016-2021, there was a 27% rate increase in women giving birth with pregestational diabetes ¹. In addition, there are racial disparities associated with pregestational diabetes, with the lowest rates in Caucasian women and the highest rates in Black, Native American, and Hispanic women ².

Pregestational diabetes is also comprised of both Type 1 and Type 2 diabetes mellitus; however, these are the result of vastly different mechanisms. Similar to the pathophysiology of gestational diabetes in pregnancy, Type 2 diabetes is related to insulin resistance (as opposed to insulin deficiency in Type 1) and is closely associated with obesity and sedentary lifestyle. Because of the characteristics, Type 2 diabetes is likely to respond to lifestyle interventions for improvement.

Lifestyle modification is an important part of blood glucose management in pregnancy. Although the primary focus is typically diet modification, physical activity is also associated with improved glucose control ⁴⁻⁵. Andersen et al. followed 14 women with diet-controlled gestational diabetes in Denmark and found reduced mean glucose in patients with 20 minutes of walking after each meal ⁶. In addition, short periods of post-prandial walking were found to have similar effect on glucose concentrations compared to longer strenuous activity ⁷. Outside of pregnancy, postprandial walking was found to be superior to pre-meal exercise for management of Type 2 diabetes ⁸.

Optimization of glucose levels in pregnancy can reduce the risk of several adverse outcomes, which include miscarriage, congenital birth defects, macrosomia, intrauterine fetal demise, and neonatal morbidity ². Traditionally in pregnancy, patients with diabetes would monitor blood glucose levels four times daily: fasting and then 1- or 2-hours postprandial. However, more recently, continuous glucose monitoring (CGM) has become more popular and readily available. In a cohort of patients using CGM, Bartal et al. found that the proportion of the time glucose levels were within what is considered acceptable range, referred to as time in range was associated with neonatal outcomes ³. Specifically, patients whose time in range was below 70% had worse neonatal outcomes than those with time in range at or above 70%.

We hypothesize that post-prandial walking will improve time in range on continuous glucose monitoring, as well as maternal and neonatal outcomes in pregnant patients with Type 2 diabetes. As an initial step in testing this hypothesis, we will conduct a randomized controlled trial to limit bias in evaluating these hypotheses. A FitBit will be provided to both groups to assess adherence to the walking regimen.

Each year, approximately 400 pregnant women with Type 2 diabetes are followed at Eastern Virginia Medical School Maternal Fetal Medicine. This would be the first randomized-controlled trial focusing on post-prandial walking utilizing continuous glucose monitoring and FitBit data in this US patient population.

2. Specific aims:

Aim 1. To examine the effect of post-prandial walking on time in range on CGM in pregnant patients with Type 2 diabetes

3. Study design:

We propose a randomized controlled trial of women with singleton pregnancies who present with a diagnosis of pre-gestational Type 2 diabetes. The participants will be randomized to the intervention group (post-prandial walks + standard care) or control group (standard care alone which includes the usual counseling regarding activity) in a 1:1 ratio. The participant will be randomized by a number-generating

computer software after recruitment at the gestational diabetes education class. All participants will receive a continuous glucose monitor and basic model FitBit for use and data collection.

Inclusion criteria

- Singleton gestation
- Known diagnosis of Type 2 diabetes OR meets new diagnosis of Type 2 diabetes in the first trimester (up through 13 weeks and 6 days)⁹
- Age ≥ 18 and <50 years
- Gestational age <32 weeks 0 days gestation

Exclusion criteria

- Non-English as primary language.
- Inability to participate in 20 minutes of walking at a time
- Known or suspected fetal anomaly or aneuploidy
- Prisoners
- Management of diabetes outside of Eastern Virginia Medical School Maternal Fetal Medicine

Because we are a tertiary care center, some individuals may be seen at several different time points in the pregnancy at time of recruitment. All of these participants can be included for recruitment until 32 weeks 0 days gestation.

3.1 Postprandial walking:

Post-prandial walking group

Participants will be instructed to walk specifically for 20 minutes after each meal (breakfast, lunch, and dinner).

Control group

Participants will receive the usual counseling regarding physical activity, which does not include post-prandial walking.

Both groups

All participants will be encouraged to continue exercise per the U.S. Department of Health and Human Services Physical Activity Guidelines for Americans and the American College of Obstetricians and Gynecologists recommendations, which includes at least 150 minutes of moderate intensity aerobic activity per week during pregnancy. Given these recommendations, post-prandial walking is minimal risk to the patient and is an activity that patients may choose to do even outside of this study.

Both groups will have a fasting blood draw and urine sample at enrollment and between 34-36 weeks gestation in the outpatient setting, typically less than 25cc blood, to test for metabolomics.

Both groups will also have an estimation of body composition at enrollment and between 34-36 weeks gestation using bioelectrical impedance analysis (BIA), which introduces (non-invasively) a current into the body passing through a source electrode and a detector electrode, located on both hands and feet. BIA measures Resistance and Reactance and their vector relationship Impedance. Based on predictive equation, BIA estimates fat mass, fat-free mass, lean soft tissue, total body, intracellular, extracellular water, and phase angle. There are no known risks or discomforts related to the BIA. Minor discomfort is associated with the placement and removal of the electrodes on the skin.

4. Procedures:

4.1 Recruitment and Screening:

Subjects will be screened and offered recruitment if they meet inclusion and exclusion criteria. This will occur at the EVMS Maternal Fetal Medicine Diabetes Program Clinic. The length of active participation will be variable depending on when they enter our care, and our intervention will continue throughout pregnancy. Our primary outcome length will last 2 weeks, but from randomization to postpartum, it can be up to 37 weeks (almost the entire pregnancy). No direct involvement is needed from the patient after delivery. However, data collection for secondary outcomes via chart review will continue to be collected through 2 weeks postpartum.

4.2 Consenting process:

Patients will be approached at the EVMS Maternal Fetal Medicine Diabetes Program. The patients will be informed that the purpose of the study is to evaluate the effect of physical activity on glucose control and that all participants will receive a FitBit Inspire 3 and continuous glucose monitor (Dexcom G7). The patients will be informed that the groups will receive two different types of counseling regarding physical activity. A patient may be withdrawn from the study if a provider outside of the research team no longer deems that participation is in the best interest of the patient. Participation in this research study will not affect any other aspect of the patient's care. The patient may withdraw from the study at any point without affecting her care. No inducements will be offered to terminate a pregnancy. Those engaged in this study will not take any part in decisions regarding termination of pregnancy and if the patient desires termination or questions the viability of the pregnancy, the patient will be referred to a non-investigator for appropriate care.

Due to the risk of introducing bias when divulging the details of the intervention group procedures to the control group, authorized deception will be utilized during the consent process. A general overview of the study that focuses on standard of care will be provided to the patients initially. If the patient is randomized to the intervention group, they will be provided with a second consent form outlining the randomization to 20 minute postprandial walks. Two separate consent forms will therefore be used: one for all participants prior to randomization, and another for the intervention group only outlining the specifics of the postprandial walk intervention.

5. Randomization:

This will be a randomized-controlled trial 1:1. Randomization to each group will be conducted via the REDCap randomization module.

6. Outcomes:

Our primary outcome is the time in range (via CGM data) during the management of Type 2 diabetes in pregnancy between 34 and 36 weeks gestation. We chose this primary outcome because it is at the time of peak insulin resistance and time in range is more closely associated with pregnancy outcomes as compared to other means of monitoring glucose control.

Secondary outcomes include FitBit data (duration of postprandial walk (in minutes), sleep duration, baseline heart rate, maximal heart rate during walks, frequency of aerobic exercise per week), CGM data (mean glucose level, glucose excursions, fasting blood sugar), total daily insulin dose, fetal demise, fetal growth restriction, preeclampsia, placental abruption, mode of delivery (cesarean or vaginal delivery), indication of cesarean delivery, presence of shoulder dystocia (for vaginal deliveries), quantitative blood loss (QBL mL), postpartum hemorrhage (QBL > 1000 mL), infection (either chorioamnionitis or postpartum endometritis prior to discharge), birth weight (gram), APGAR scores, neonatal infection (defined as sepsis, fever, positive cultures, or a suspicious clinical course that warranted antibiotics treatment), respiratory distress syndrome, necrotizing enterocolitis, and neonatal intensive care unit admission (NICU), and days in NICU. Other secondary outcomes will include metabolomic markers collected from the urine and blood, as well as body composition data.

We will also collect demographic and clinical characteristics including maternal age, gestational age at delivery, race, ethnicity, insurance, marital status, history of preterm birth, parity, and number of previous cesarean or vaginal delivery.

Chart review for secondary outcomes and demographic/clinical characteristics will be completed through Allscripts, EPIC, and Powerchart.

7. Data Gathering and Safety:

The FitBits, continuous glucose monitors, and all supplies for the patient will be paid for with no cost to the patient or the patient's insurance company. The [name] Discretionary Research Fund is covering the cost of the FitBits and CGMs. For the Dexcom G7, it is recommended that the sensor be changed every 7 days, which will be performed by the patient. Therefore, the sensor will need to be changed between 8 and 37 times throughout the study period, dependent upon what gestational age the patient was enrolled.

The research team will gather the data from the continuous glucose monitors via the share function, similar to how the data is shared to the clinical team.

The primary outcome will focus on the 34 through 36 week gestation data. However, the data from the rest of the subject's participation will be included in the secondary outcomes.

There will be two blood draws: at enrollment and again between 34 and 36 weeks gestation. A urine collection will also be performed at these times. These will be collected at an already scheduled clinic appointment.

Therefore, no additional appointment will be needed for this. It will be drawn by phlebotomy staff or research nurses. It will be kept refrigerated, processed within 24 hours, and kept in -70 degree freezer in a secured area. After collection, samples will be run and kept in a separate repository for potential future use. This will be paid by the [name] Discretionary Research Fund. There will be no cost to the patient.

The study dataset and ID key will be stored in REDCap in separate projects due to inclusion of data from the EMR.

8. Sample size calculation: Time in range in pregnant patients with pre-gestational diabetes is 66.3% with a standard deviation of 21.3% ³. We assume that 20 minutes of postprandial walking after each meal will decrease the mean glucose by 30%. Therefore, assuming a 30% improvement in time in range, with a power of 80% and alpha of 0.05, 18 mother/neonate pairs per group would be needed to reach statistical significance. Assuming a 10% loss to follow up rate, a total of 40 mother/neonate pairs will be included in the study.

9. Statistical analysis: Descriptive statistics will be provided first for describing the subjects' demographic and clinical characteristics. Fisher's exact or Chi Squared test will be used to compare categorical variables and the Student t-test or Man-Whitney U test will be used to compare numerical variables.

References:

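### Entry is open at any gestation below 32 weeks but the outcome is fixed at 34–36 weeks; naming gestational age at randomisation and adjusting for it would be a cheap gain in precision and interpretability.

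*Protocol*

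**What the plan says.** - **Entry.** The inclusion criteria in Section 3 require "Gestational age <32 weeks 0 days gestation" and set no lower limit. The paragraph after the exclusion criteria explains that a tertiary centre first sees women at different stages of pregnancy, and adds: "All of these participants can be included for recruitment until 32 weeks 0 days gestation".
- **Duration.** Section 4.1 recognises the consequence: "The length of active participation will be variable depending on when they enter our care, and our intervention will continue throughout pregnancy". It puts the longest span from randomisation to postpartum at 37 weeks. Section 7 gives 8 to 37 weekly sensor changes, depending on gestation at enrolment.
- **Outcome.** Section 6 defines the primary outcome as "time in range (via CGM data) during the management of Type 2 diabetes in pregnancy between 34 and 36 weeks gestation". Body composition and metabolomic markers are secondary outcomes. Section 3.1 has them measured at enrolment and again at 34–36 weeks.
- **Allocation.** Section 5 gives a 1:1 ratio and one further sentence: "Randomization to each group will be conducted via the REDCap randomization module". No stratification factor appears there or in Section 3.
- **Baseline variables.** The list in Section 6 includes "maternal age, gestational age at delivery, race, ethnicity, insurance, marital status". Gestational age at delivery is named; gestational age at entry is not.
- **Analysis.** Section 9 states two-group tests only: t-test or Mann-Whitney for numerical variables, Fisher's exact or chi-squared for categorical ones.

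**The concern.** With the outcome window fixed, gestational age at entry determines how long a woman in the walking arm has walked before she is measured. It also sets the gestation of her enrolment impedance, blood and urine samples, and may go with how long she has been under this clinic's care. It is therefore a plausible predictor of time in range and a strong candidate predictor of gestation-dependent quantities such as body water and fat mass.

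In a trial of 40, chance can leave the arms visibly different on such a variable. The protocol names no stratum to limit this and no covariate to absorb it. Its list also names a post-randomisation gestational age (at delivery) while leaving out the baseline one. At stake are some avoidable noise in the primary comparison, and enrolment samples that are hard to interpret unless gestation is taken into account.

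**Working it through.** **Inputs from the protocol.** Latest entry 31w6d (Section 3); outcome window from 34w0d (Section 6); longest span 37 weeks (Section 4.1); mean time in range 66.3%, SD 21.3%, 30% relative improvement, power 80%, alpha 0.05 (taken as two-sided), 18 per group, 40 in total (Section 8).

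**1. The plan's own sample size.**
- Difference = 0.30 × 66.3 = 19.89 points.
- n per group = 2 × (21.3 × (1.960 + 0.842) / 19.89)² = 18.00, and 18 / 0.90 = 20 per group, 40 in total. The stated figures reproduce.
- Normal-approximation power at 18 per group is 80.0%. There is no slack; the t-based power is 77.7%.

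**2. Walking before the primary window.**
- Shortest: 34w0d − 31w6d = 15 days, or 2.1 weeks.
- Longest: if the 37 weeks end at a 40-week delivery (assumed), entry is at week 3 and walking lasts 34 − 3 = 31 weeks. If they end two weeks postpartum, entry is at week 5 and walking lasts 34 − 5 = 29 weeks.
- The range is therefore about 2 to about 30 weeks.

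**3. Interval between the two sample sets.** Take entry at week 4 (illustrative) against entry at 31w6d.
- Both sampled at 34w0d: 30 against 2.1 weeks, a 14-fold difference.
- Both sampled at 36w0d: 32 against 4.1 weeks, a 7.7-fold difference.

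**4. Chance imbalance.** Assume half of the 40 women are late entrants, with 20 per arm and no stratification. The number of late entrants in one arm is hypergeometric.
- Variance = 20 × 0.5 × 0.5 × 20/39 = 2.56; SD = 1.60.
- The gap between arms in the proportion late has SD 2 × 1.60 / 20 = 0.16.
- A gap of at least 20 percentage points occurs in 34% of trials, and of at least 30 points in 11%.

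**5. Effect on the estimate.** Assume late and early entrants differ by 5 to 15 points in time in range.
- Typical (1 SD) shift: 0.16 × 5 to 0.16 × 15 = 0.8 to 2.4 points.
- Tail case, a 30-point gap: 0.30 × 5 to 0.30 × 15 = 1.5 to 4.5 points.
- Standard error of the treatment difference: 21.3 × √(2/20) = 6.7 points with 20 per arm, 21.3 × √(2/18) = 7.1 with 18.

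**6. What adjustment could recover.** A half-and-half split with difference D contributes D²/4 to the outcome variance, which is 21.3² = 453.7.

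| D (assumed) | D²/4 | Residual SD | Standard error, 18 per arm | Power |
|---|---|---|---|---|
| none | 0 | 21.3 | 7.10 | 80.0% |
| 5 points | 6.25 | 21.15 | 7.05 | 80.5% |
| 15 points | 56.25 | 19.94 | 6.65 | 84.9% |

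Power is by the normal approximation, Φ(19.89 / SE − 1.96). The loss of one degree of freedom is ignored.

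**The case against.** The case against is substantial.

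- **The wide window is deliberate.** The protocol gives its reason, says that duration varies, measures everyone at the same gestation and continues the intervention throughout pregnancy. Every woman in the walking arm has at least 15 days assigned before measurement. This stands: nothing here contradicts itself.
- **Randomisation already deals with entry age in expectation.** A reader might infer that late entry confounds the walking effect with time in care. The protocol does not support that. Chance imbalance is reflected in the standard error and the unadjusted test keeps its error rate. Entry age is not the same as time in care either, since a woman already attending the clinic may be randomised late.
- **Entry age is not lost.** The Section 6 list is introduced as an inclusion of examples, and gestation must be known to check eligibility. The gap is only that it is not named as a baseline variable or covariate.
- **Stratification is not excluded, and covariates may sit in an analysis plan that is not shown.** Section 5 is silent rather than explicit. On covariates the point rests on what Section 9 does state, which is unadjusted tests. Stratification cannot be added by an analysis plan once allocation has started.
- **Change from enrolment is not defined as an outcome.** Correct. The interval comparison above matters only if change is analysed, but the enrolment values come from widely differing gestations in any case.
- **The fix leaves the 2-to-30-week spread in place.** Also correct. Stratification and adjustment act between arms, and the variation within the walking arm remains.

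**Conclusion.** The point holds as a worthwhile improvement, not as an error that threatens validity. Certain from the document: entry at any gestation below 32w0d, a fixed 34–36-week outcome, about 2 to about 30 weeks of prior walking, no named stratum, and unadjusted tests.

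The size rests on two assumptions that the protocol does not supply: a half-and-half split of early and late entrants, and a 5-to-15-point difference between them in time in range. Under these, the typical shift of 0.8 to 2.4 points is small beside a standard error of about 7 and a planned difference of 19.9. The power gain is half a point at the low end and about five points at the high end. The case is strongest for body composition and metabolomics, where the gestation of the enrolment sample bears directly on what the value means.

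A reader might also infer that late entrants dilute the effect and leave the trial underpowered. The protocol gives no relation between weeks of walking and time in range, so that cannot be concluded. What can be said is that Section 8 assumes one common effect whatever the duration.

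**What to change.** - **Section 6:** name gestational age at randomisation among the baseline characteristics.
- **Section 9:** include it as a continuous covariate in the time-in-range comparison and in the body composition and metabolomic comparisons, in place of the unadjusted tests for those outcomes.
- **Section 5, only if enrolment has not begun:** stratify the REDCap allocation on it in two strata, with blocks of varying size. If allocation has started, the first two changes still apply.
- **Interpretation:** state that the estimate averages over widely differing durations of walking, which neither change removes.

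No change to eligibility, walking or care is needed. The cost is one degree of freedom, with little or no power gain if entry age turns out to be weakly prognostic. Stratifying with small blocks in an open trial also makes allocation slightly more predictable; varying the block size limits this.

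### Chart review closes at 2 weeks postpartum, so the full NICU stay of an infant still admitted then cannot be captured under the open-ended outcome of days in NICU

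*Protocol*

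**What the plan says.** Protocol Section 4.1 (Recruitment and Screening) sets one closing date for postnatal data: "data collection for secondary outcomes via chart review will continue to be collected through 2 weeks postpartum". The sentence before it rules out other contact: "No direct involvement is needed from the patient after delivery".

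Section 6 (Outcomes) ends its list of clinical secondary outcomes with "neonatal intensive care unit admission (NICU), and days in NICU". No window, cap or discharge rule is attached. The same section gives the source: "Chart review for secondary outcomes and demographic/clinical characteristics will be completed through Allscripts, EPIC, and Powerchart".

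Elsewhere in that list a limit is written out. Maternal infection is counted as "infection (either chorioamnionitis or postpartum endometritis prior to discharge". Neonatal infection and necrotizing enterocolitis, like days in NICU, carry none.

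Section 9 (Statistical analysis) says that "the Student t-test or Man-Whitney U test will be used to compare numerical variables". Section 8 (Sample size calculation) says that "a total of 40 mother/neonate pairs will be included in the study".

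**The concern.** Days in NICU is a duration that can outlast a 2-week window. The protocol closes the only described source of the data at 2 weeks, yet names the outcome as if the whole stay were counted. A reader of the results would take it as length of stay. For any infant still admitted when collection closes, the value obtained would be something else.

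Neonatal results belong to the hypothesis in Section 1, which expects walking to improve time in range "as well as maternal and neonatal outcomes in pregnant patients with Type 2 diabetes", although the only specific aim (Section 2) is time in range on CGM. With about 20 infants per arm, a single long stay has visible weight in an arm mean, and the longest stays are the ones lost. The collection period is fixed in the protocol, and an analysis plan cannot restore days that were never collected.

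**Working it through.** **1. The passages side by side.**
- Section 4.1: collection by chart review stops at 2 weeks postpartum, with no contact after delivery.
- Section 6: days in NICU is unlimited, and chart review is the source.
- No other section extends neonatal review or says how a stay still open at 2 weeks is entered.

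At most about 14 days can therefore be observed. For a true stay of L days, the observable part is min(L, 14). If L exceeds 14, the entry is either about 14 or missing.

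**2. The plan's own figure, used here only for the arm size.** Section 8 gives a mean of 66.3%, an SD of 21.3%, a 30% improvement, 80% power and alpha 0.05 (taken as two-sided). The difference is 0.30 × 66.3 = 19.89 points. The normal approximation gives 18.002 per group, against 18 stated. Then 36 / (1 − 0.10) = 40. So n is 18 (required) to 20 (enrolled) per arm. Nothing below questions that calculation.

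**3. Effect on an arm mean if long stays are cut at 14 days.** The documents give no NICU rate or stay length, so the true stay L, the number of cut stays k and the number admitted are all assumptions. With non-admitted infants counted as 0, the arm mean falls by k(L − 14)/n:

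| Assumed true stay | k = 0 | k = 1 (n = 20 to 18) | k = 2 (n = 20 to 18) |
|---|---|---|---|
| 21 days | 0 | 7/20 to 7/18 = 0.35 to 0.39 | 0.70 to 0.78 |
| 28 days | 0 | 14/20 to 14/18 = 0.70 to 0.78 | 1.40 to 1.56 |
| 40 days | 0 | 26/20 to 26/18 = 1.30 to 1.44 | 2.60 to 2.89 |

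If only admitted infants are averaged (8 down to 4 per arm, assumed) and one stay is cut, the fall is:
- 21 days: 7/8 to 7/4 = 0.88 to 1.75 days
- 28 days: 14/8 to 14/4 = 1.75 to 3.50 days
- 40 days: 26/8 to 26/4 = 3.25 to 6.50 days

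**4. Effect on an arm mean if the stay is left missing.** Dropping one infant with stay L from an arm whose other infants average m lowers the mean by (L − m)/n. The value of m is unknown. Its smallest possible value, m = 0, gives the upper limit L/n. For L = 28 that is 28/20 to 28/18 = 1.40 to 1.56 days.

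**5. Effect on the rank test.**
- *Stays cut.* If no other stay reaches 14 days, cutting changes no ordering except among the cut infants, who become tied. The U statistic then moves by at most (cut infants in arm A) × (cut infants in arm B)/2. With cut infants in one arm only, that is 0. With one in each arm it is 0.5, out of 18 × 18 = 324 to 20 × 20 = 400 pairs (0.15% to 0.13%). With two in each arm it is 2.
- *Stays missing.* Every comparison involving the dropped infant disappears: 18 of 324 or 20 of 400 pairs for one infant. The near-immunity of the rank test therefore holds only if stays are cut.

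**The case against.** The strongest reply is that the two sections can be read together. Section 4.1 sets a general window, almost every outcome in Section 6 lacks a limit of its own, and so the window governs the list and the outcome is simply NICU days up to 2 weeks. That reading is available. However, no sentence states it, the outcome name does not show it, and where Section 6 wants a limit (maternal infection) it writes one. If this is what was meant, the remedy is a new name.

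It can also be said that the handling of open stays, zeros for non-admitted infants and deaths belongs in the analysis plan, which is not at hand. That is right for those details, but not for the closing date of data collection, which is protocol content.

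The sizes above rest wholly on assumed stays, and the largest (6.50 days) combines the longest assumed stay with the smallest assumed number admitted. The trial takes singletons only and excludes known or suspected fetal anomaly or aneuploidy, which may make long stays less common. The documents do not quantify this. All of that stands and limits the weight of the numbers.

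Three stronger readings are tempting and are not supported:
- *Long stays will be recorded as 14 days.* The protocol states no such rule, and missing values are as consistent with the text.
- *The cut-off favours one arm.* The same window applies to both arms, and no direction can be derived.
- *Only days in NICU needs attention.* Neonatal infection and necrotizing enterocolitis also have no stated limit, and the cut-off could miss a later event in the same stay. The documents do not show that 2 weeks is adequate for them.

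**Conclusion.** The point holds in a limited form. The collection window in Section 4.1 cannot deliver the full days in NICU listed in Section 6 for an infant still admitted at 2 weeks, and the protocol does not say whether such a stay is cut or left missing. This is a stated rule that makes a listed outcome incomplete, rather than a detail left for later.

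The effect may be nil. If one infant per arm is affected and stays of 21 to 40 days are assumed, cutting shifts an arm mean by 0.35 to 1.44 days over 18 to 20 infants, and by more if only admitted infants are averaged. Reported means and the t-test are exposed. The Mann-Whitney test hardly is, provided stays are cut and no uncut stay reaches 14 days. The primary CGM outcome and the sample size are unaffected. It is a low-severity point worth correcting because the correction is cheap.

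**What to change.** Amend Section 4.1 so that chart review for days in NICU runs, in both arms, to the later of 2 weeks postpartum or NICU discharge or death. State in the same sentence whether neonatal infection and necrotizing enterocolitis follow the 2-week window or the NICU stay.

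If a 2-week limit is intended, leave the window as it is, rename the outcome in Section 6 *NICU days through 2 weeks postpartum*, and make the same statement for the two other neonatal outcomes.

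The first option costs a sentence, a few later chart look-ups for infants still admitted at 2 weeks, and approval of a slightly longer data-collection period. It needs no patient contact. The second costs only wording, but gives up length of stay as an outcome.

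### Does giving the walking arm alone a second consent form after randomisation remove women who decline it from the comparison?

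*Protocol*

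**What the plan says.** Section 4.2 of the protocol sets up a two-stage consent under authorised deception, so that controls do not learn of the walking regimen. At the first stage, "A general overview of the study that focuses on standard of care will be provided to the patients initially". Women are then randomised 1:1 (section 5), and after that: "If the patient is randomized to the intervention group, they will be provided with a second consent form". The two forms are described as "one for all participants prior to randomization, and another for the intervention group only".

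At first consent the women are not wholly uninformed. They are told that the study concerns physical activity and glucose control, and "The patients will be informed that the groups will receive two different types of counseling regarding physical activity". The exclusion criteria in section 3 remove women with "Inability to participate in 20 minutes of walking at a time".

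Section 4.2 names two ways out of the trial. A provider outside the research team may judge that participation is no longer in the patient's interest, or the woman may leave by her own choice: "The patient may withdraw from the study at any point without affecting her care". Refusal of the second form is not mentioned, either as an exit or as something compatible with staying in.

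**The concern.** A consent form can be refused. This one is offered after allocation and to one arm only, so it creates a point of possible loss that the control arm does not have. If refusal were handled as withdrawal, the walking arm would keep only women willing to follow the schedule, while the control arm would keep willing and unwilling women alike. If willingness is related to glucose control, the difference in time in range would carry a selection effect.

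Refusal is not far-fetched. Section 3.1 asks for a 20-minute walk after each of three meals, which is 3 × 20 × 7 = 420 minutes a week. The general encouragement given to both arms is "at least 150 minutes of moderate intensity aerobic activity per week during pregnancy". The ratio is 420/150 = 2.8, and the woman does not know of this schedule when she signs the first form.

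Nor could a later analysis plan repair such a loss. The primary outcome is continuous glucose monitoring (CGM) at 34 to 36 weeks. If a woman left and stopped sharing her sensor data, that outcome would not exist.

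**Working it through.** **1. What the text does with a woman who refuses the second form**

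| Question | Where | What it says |
|---|---|---|
| Who signs the first form? | 4.2 | Everyone, before randomisation |
| What does the second form cover? | 4.2 | The details of the walks only |
| Who gets the CGM and FitBit? | 3 | All participants |
| Who has blood, urine and body composition measured? | 3.1 | Both groups |
| What ends participation? | 4.2 | An outside provider's judgement, or the woman leaving the study |
| Are participants replaced? | – | Not mentioned anywhere |

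No data collection is tied to signing the second form, and declining it is neither of the listed exits. Read as written, the protocol removes no decliner. Retention is an inference from these lines, not a stated rule.

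**2. The plan's own sample size (section 8)**

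Inputs: mean 66.3, SD 21.3, 30% relative improvement, power 80%, alpha 0.05 (taken as two-sided), 10% loss.

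- Planned effect: 0.30 × 66.3 = 19.89 points.
- Normal approximation: n = 2 × (1.960 + 0.842)² × (21.3/19.89)² = 18.0 per group.
- 18/0.9 = 20 per group, 40 in total.

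The stated figures reproduce. By the t-test, power is 0.777 at 18 per group and 0.821 at 20.

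**3. Size of the bias if decliners were dropped or replaced**

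The documents give neither a refusal share p nor a time-in-range gap D between accepters and decliners. Both are assumed: p from 10% to 20%, D from 10 to 20 points.

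Bias = p × D. With no true effect, the two-sided t-test at SD 21.3 rejects as follows:

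| p | D | Bias (points) | Replaced, 20 v 20 | Replaced, 18 v 18 | Leave unreplaced, 18(1−p) v 18 |
|---|---|---|---|---|---|
| 10% | 10 | 1.00 | 5.2% | 5.2% | 5.2% |
| 15% | 15 | 2.25 | 6.2% | 6.1% | 6.0% |
| 20% | 20 | 4.00 | 8.9% | 8.5% | 8.1% |

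The standard error is 21.3 × √(2/18) = 7.10 at 18 per arm and 21.3 × √(2/20) = 6.74 at 20. The equal-arm columns apply only if decliners are replaced. The bias is zero if nobody refuses or if D = 0, and it changes sign if decliners have the better control.

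**4. Power**

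If decliners stay in and get no benefit, the effect shrinks to 19.89 × (1 − p): 17.9 points at 10% and 15.9 at 20%. Power at 18 per arm is then 0.688 and 0.586, and at 20 per arm 0.736 and 0.634. If they leave unreplaced, on top of the planned 10% loss, the comparison is 16.2 v 18 or 14.4 v 18, with power 0.753 and 0.725.

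**The case for a change.** The strongest case for acting is that this is a matter of trial conduct, not of analysis. An analysis plan can name the population but cannot recover CGM readings that were never taken. Follow-up can also be long: section 4.1 allows up to 37 weeks from randomisation to postpartum. A site that treats refusal as withdrawal would lose the primary outcome in one arm only, in a trial where the whole loss allowance is 2 of 20 women per arm. One sentence in section 4.2 would prevent this at almost no cost.

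Part of this stands. The sequence does open a refusal point in one arm only, the equal 10% allowance makes no separate provision for it, and lost CGM data could not be restored.

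The rest depends on a practice that the protocol does not state. The two-stage consent is a deliberate trade: it keeps controls from learning of the walks and taking them up, and nobody proposes to reverse it. What remains is whether the first consent stays in force when the second is refused. That is ordinary consent-form content, and the forms are not among the documents at hand, so their silence cannot be assumed. The analysis population and the reporting of refusals are ordinary SAP content. The 2.8-fold ratio is also weaker than it looks, because the 150 minutes is a minimum at a stated intensity and the walks have no stated intensity; it says nothing about how many women would refuse.

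**Conclusion.** No change to the plan follows. The protocol is silent on women who decline the second form, but its wording favours keeping them, and nothing in it removes or replaces them. A team following the text would leave such a woman in her allocated arm with data collection continuing under the first consent, unless she withdrew that too.

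Harm needs three things that the documents do not supply: an appreciable refusal share, a gap in glucose control between accepters and decliners, and a practice of dropping or replacing decliners. Under the assumed ranges the bias is 1 to 4 points against a planned 19.9. At the midpoints the error rate is about 6%. The highest figure, 8.9%, needs 20% refusal, a 20-point gap (as large as the planned effect), replacement of every decliner and no other loss.

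The conclusion rests on the visible text alone. It would change if the consent forms equated refusal of the second form with withdrawal from the study.
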